6.2 Surgical/Medical History and Alopecia Areata History

Medical history will be coded according to the Medical Dictionary for Regulatory Activities (MedDRA), Version 24.1.

Surgical and medical history will be summarized by system organ class (SOC) and preferred term (PT) on the safety analysis set. A subject who experienced the same surgical and medical history event multiple times will be counted only once for the corresponding PT. Similarly, if a subject experienced multiple surgical and medical history events within the same SOC, the subject will be counted only once for that SOC. Surgical and medical history events will be sorted alphabetically

by SOC and within each SOC the PT will be presented by decreasing order of total frequency within each SOC.

Disease history of the subject's AA, including the AA subtype at initial diagnosis and current episode diagnosis, any prior AA treatment taken, and current involvement of fingernail, eyelash, eyebrow, and facial hair will be summarized descriptively.

A listing of all surgical and medical history events will be provided. In addition, a listing of AA disease history will also be provided.

7 SUBJECTS ACCOUNTABILITY

7.1 Disposition of Subjects

All subjects who provide informed consent will be accounted for in this study. The number of subjects screened, enrolled, screen failed and the reason for screen failure will be presented for all screened subjects for each cohort and overall in the DB Treatment Period. The percentage of subject enrolled and screen failures will be calculated using the number of subjects screened in each cohort as denominator. The percentage of reasons for screen failure will be calculated using the number of screen failures in each cohort as denominator.

For the DB Treatment Period, the numbers and percentages of randomized subjects included in each analysis set (Randomized, FAS, modified FAS, PPS, and Safety) will be presented for each DB Treatment Period group and overall.

Study DB Treatment Period completion status and the reason for DB Treatment Period treatment discontinuation will also be presented for each DB Treatment Period treatment group and overall. The percentage of reasons for DB Treatment Period study discontinuation will be calculated using the number of subjects randomized in the DB Treatment Period as denominator.

The numbers and percentages of subjects enrolled into OLE period and subjects not enrolled into OLE Period will be presented for each DB Treatment Period treatment group and overall.

Subject disposition in the OLE Period and the full study (DB Treatment Period and OLE Period) will be summarized using frequency counts and percentages, including: OLE Period completion status, reason for treatment discontinuation in the OLE Period, full study completion status and reason for study discontinuation in the full study (overall and by OLE Period treatment group). The percentage of reasons for OLE Period study discontinuation will be calculated using the number of subjects randomized in the OLE Period as denominator.

A listing of subject's disposition will be provided. Information on first screening for subjects who were rescreened, including the rescreened subject identifier, will be presented under the first

screening subject identifier. A listing of subject's randomization information and a listing of subjects included in each of the study populations will also be provided.

In order to describe the impact of COVID-19, subjects discontinued from the study due to COVID-19 as the primary reason will be summarized in the above disposition table. The specific reasons for subjects discontinued due to COVID-19 such as subject decision, subject self-isolation, non-compliance with protocol, transportation issue, site restrictions, physician decision, site closed, lack of drug at site, sponsor decision, and severity of COVID-19 infection will be presented in the above disposition listing.

7.2 Protocol Deviations

PDs with a start date before the date of first dose in OLE will be considered a DB PD while PDs with a start date on or after the date of first dose in OLE will be considered an OLE PD.

A blinded data review will be conducted before the primary database lock by the Medical Monitor and Sponsor to classify each PD occurring during the DB Treatment Period as 1) important or non-important and 2) major or minor (refer to the PD Management Plan [PDMP]). Another data review will be conducted before the final database lock by the Medical Monitor and Sponsor to classify each PD occurring during the OLE period as 1) important or non-important and 2) major or minor (refer to the PDMP).

During the review conducted before the primary database lock for DB Treatment Period, major PDs potentially having an impact on the SALT I-related primary and secondary efficacy endpoints will be identified by the Medical Monitor and Sponsor and will lead to the exclusion from the PPS. These PDs might include, but are not limited to:

- Violation of eligibility criteria
- Receiving incorrect study treatment
- Compliance with study treatment < 80%
- Chronic use of prohibited medication while on study treatment

The number of events and the frequency count and percentage of subjects with at least one important PD, with a least one major PD, with at least one major PD potentially having an impact on the SALT I-related primary and secondary efficacy endpoints, and with at least one PD associated with COVID-19 will be summarized for the DB Treatment Period by treatment group, deviation category, and deviation sub-category using the randomized set. Important PDs, major PDs, and PDs related to COVID-19 will be summarized similarly overall using the randomized set and for the OLE period using the OLE SAF.

A listing of all protocol deviations will be provided. Important PDs, major PDs, major PDs potentially having an impact on the on the SALT I-related primary and secondary efficacy endpoints, and COVID-19 related PDs will be flagged in this listing.

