6.3. Dosage and Administration

Subjects will self-administer study drug, except on study visit days, from Day 1 until the day prior to the Week 52 visit. Tablets (etrasimod 1 mg, etrasimod 2 mg, or placebo) are to be taken once daily with water (either with or without food) at approximately the same time each day, preferably in the morning according to the schedule described in [Table 2](#) (Cohort 1) and [Table 3](#) (Cohort 2).

Table 2: Study Drug Dosage and Administration for Cohort 1

Randomization Assignment ^a	Double-Blind Treatment Period		Open-Label Extension Period	
	Day 1 to Week 24 Visit ^b	Week 24 Visit to Week 25 Visit	Week 24 Visit to Week 25 Visit	Week 25 Visit to Week 52 Visit ^{c,d,e}
Placebo	1 × placebo		1 × 2 mg	1 × 2 mg + 1 × 1 mg or 1 × 2 mg ^f
2 mg etrasimod	1 × 2 mg		1 × 2 mg	1 × 2 mg + 1 × 1 mg or 1 × 2 mg ^f

^a Randomization assignment refers to treatment assignment in the Double-Blind Treatment Period.

^b No double-blind treatment is to be administered at the Week 24 visit. Treatment in the Open-Label Extension Period will start at Week 24 after all assessments of the Double-Blind Period are completed.

^c Subjects entering the Open-Label Extension Period (Week 24 visit) before implementation of Amendments 2.0 and 2.1 will transition to 3 mg once daily at their next study visit. Subjects entering the Open-Label Extension Period (Week 24 visit) after implementation of Amendments 2.0 and 2.1 will receive etrasimod 2 mg from the Week 24 visit to the Week 25 visit and will transition to etrasimod 3 mg at the Week 25 visit.

^d No treatment is to be administered at the Week 52 visit.

^e In case of study drug interruption of etrasimod 3 mg, treatment will be re-initiated by starting with etrasimod 2 mg for 1 week before transitioning to etrasimod 3 mg. Holter monitoring, as described in Section 10.5.7.5, must be performed any time a subject transitions from 2 mg to 3 mg etrasimod.

^f Subjects already in the Open-Label Extension Period at the time of Amendments 2.0 and 2.1 implementation may be allowed to continue on etrasimod 2 mg at the Investigator's discretion provided that they have achieved a SALT I score ≤ 20.

SALT I, Severity of Alopecia Tool I

Table 3: Study Drug Dosage and Administration for Cohort 2

Randomization Assignment ^a	Double-Blind Treatment Period		Open-Label Extension Period	
	Day 1 to Week 1 Visit	Week 1 Visit to Week 24 Visit ^{b,c}	Week 24 Visit to Week 25 Visit	Week 25 Visit to Week 52 Visit ^{c,d}

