4.3 Windowing Conventions

When available, visits will be analyzed as scheduled (refer to protocol Appendices 1 and 2). ET and/or unscheduled/retest measurements will only be included if a scheduled measurement is not available, and the ET or unscheduled/retest measurement falls within the analysis visit windows as described in [Table 1](#).

If there is more than one retest, unscheduled or ET assessment for a given analysis visit, the assessment closest to the target day will be retained for data summary of that visit; if there are 2

observations with equal distance to the target day, then the later one will be retained. All data from scheduled, retest, unscheduled, and ET visit assessments will be listed.

Table 1: Analysis Visit Windows

Analysis Visit	Target Study Day	Visit Window (Period Day)
DB Treatment Period		
DB Baseline	1	Refer to DB Treatment Period Baseline definition in Section 4.1
Week 1 (Cohort 2 only)	Day 8	Post first dose – Day 11
Week 2	Day 15	Cohort 1: Post first dose – Day 21 Cohort 2: Day 12 – Day 21
Week 4	Day 29	Day 22 – Day 42
Week 8	Day 57	Day 43 – Day 70
Week 12	Day 85	Day 71 – Day 98
Week 16	Day 113	Day 99 – Day 126
Week 20	Day 141	Day 127– Day 154
Week 24*	Day 169	Day 155 – (Last treatment day + 6) in DB period for subjects never treated in OLE; Day 155 – Pre first dose in OLE for subjects treated in OLE
OLE Period **		
OLE Baseline	OLE Day 1	Refer to OLE Period Baseline definition in Section 4.1
Week 25	OLE Day 8	Post first dose in OLE – OLE Day 18
Week 28	OLE Day 29	OLE Day 19 – OLE Day 56
Week 36	OLE Day 85	OLE Day 57 – OLE Day 112
Week 44	OLE Day 141	OLE Day 113 – OLE Day 168
Week 52	OLE Day 197	OLE Day 169 – (Last treatment day + 6)
Safety Follow-up 1	Last treatment day + 14 days (± 3 days)	(Last treatment day + 7) – (Last treatment day + 21 days)
Safety Follow-up 2	Last treatment day + 28 days (± 3 days)	(Last treatment day + 22 days) - (Last contact day)

DB = Double-Blind; OLE = Open-Label Extension; SFU = Safety Follow-Up

* Week 24 is the last scheduled visit in DB Treatment Period and first scheduled visit in OLE Period.

** The days are Period Day (refer to Section 4.2) in the OLE Period.

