11.1 Adverse Events

AEs will be coded according to the MedDRA, Version 24.1, and will be summarized overall and by treatment group for across both study periods and for each study period separately.

Treatment emergent adverse events (TEAEs) are defined as any AEs with onset date during or after the first study treatment dose. See Appendix 2 for handling of completely or partially missing dates for AEs. AEs starting on the first study treatment dosing date and related to a pre-dose study assessment will not be considered as TEAE. In the case where it is not possible to define an AE as treatment emergent or not, the AE will be classified as treatment emergent.

Furthermore, TEAEs will be assigned to the DB Treatment Period or OLE Period depending on their onset date – if the AE onset date is before the date of first dose in OLE, the AE will be assigned to the DB Treatment Period AE. If the AE had an onset on or after the date of first dose in OLE, the AE will be assigned to an OLE Period. AEs starting on the Week 24 and related to a pre-dose study assessment will be assigned to DB Treatment Period.

An overall summary table of adverse events will be provided. The number of events and the frequency count and percentage of subjects who experienced an AE, TEAE, TEAE by maximum reported relationship, TEAE by maximum reported Common Terminology Criteria for Adverse Events (CTCAE) severity, serious AE (SAE), serious TEAE, TEAE leading to study drug

discontinuation, TEAE leading to study discontinuation, treatment emergent AE of Special Interest (AESI) and AE leading to death will be presented.

Of note, prior to each database lock (primary and final), AESIs will be flagged as such by the Sponsor Clinical Development/Medical teams from the subset of AEs that will have been classified programmatically as Targeted Medical Events (TMEs) based on an exhaustive list of SOCs and PTs provided by the Sponsor. The list of AEs deemed as AESIs will be finalized prior to each database lock.

Unless otherwise specified, a subject experiencing a TEAE multiple times within the same PT will be counted only once for the corresponding PT. Similarly, if a subject experiencing multiple TEAEs within the same SOC, the subject will be counted only once for that SOC. TEAEs will be sorted by decreasing order of total frequency of SOC and PT within each SOC.

Frequency and percentage of subjects who experience TEAE will be summarized by PT and also by SOC and PT.

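### SAP 7.2 splits deviations by date alone, so a deviation in a pre-dose Week 24 assessment is labelled open-label when the first open-label dose is given that same day

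*SAP*

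**What the plan says.** SAP 7.2 divides deviations by start date. Those before the date of the first OLE dose belong to the DB period; for the rest, "PDs with a start date on or after the date of first dose in OLE will be considered an OLE PD". The rule uses neither clock time nor whether the procedure came before the dose.

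The same section plans two reviews. The first is blinded, takes place before the primary lock, and is meant "to classify each PD occurring during the DB Treatment Period as 1) important or non-important and 2) major or minor". The second is held before the final lock and covers OLE deviations. PPS exclusions are tied to the first, at which major deviations that could bear on the SALT I results "will be identified by the Medical Monitor and Sponsor and will lead to the exclusion from the PPS".

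On timing, Protocol 6.3 (footnote b of Tables 2 and 3) states: "Treatment in the Open-Label Extension Period will start at Week 24 after all assessments of the Double-Blind Period are completed". SAP 4.3 confirms that "Week 24 is the last scheduled visit in DB Treatment Period and first scheduled visit in OLE Period", and SAP Table 1 ends the Week 24 window for continuing subjects just before that dose: "Day 155 – Pre first dose in OLE for subjects treated in OLE".

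For adverse events, SAP 11.1 uses a similar date split but adds an exception: "AEs starting on the Week 24 and related to a pre-dose study assessment will be assigned to DB Treatment Period".

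**The concern.** Week 24 SALT I is the primary endpoint assessment. For a subject who continues into the extension, the design puts that assessment and the first OLE dose at one visit, and so normally on one date. The date rule then sends the SALT I value to the DB period and a deviation in obtaining it to the OLE period.

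The stated purpose of the PPS analysis is to show how far major deviations influence the SALT I results. If deviations at the endpoint visit are sorted into the later period, the review that decides PPS membership may not consider them. The DB deviation tables would also be too low at that visit, and the OLE tables too high.

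A late repair would be weak. The DB analysis is run once all subjects have finished or left that period (SAP 4), and SAP 7.2 does not describe the second review as blinded. A change to PPS membership at the final lock could therefore be made with the DB results already known.

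**Working it through.** The plan gives no figure on this point, so there is nothing to reproduce. The check applies the date rule to the possible timings and then compares the sections.

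**Step 1: the rule.** Let d be the deviation's start date and t the date of the first OLE dose. SAP 7.2 gives DB if d < t and OLE if d ≥ t. A subject never dosed in the OLE has no t, so the deviation is DB.

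**Step 2: the cases.** Days 169 and 141 are the Week 24 and Week 20 targets in SAP Table 1. Day 167 is an assumed illustration.

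| Case | d | t | Label under SAP 7.2 |
|---|---|---|---|
| Deviation in Week 24 SALT I, OLE dose the same day | 169 | 169 | OLE |
| Deviation at Week 24, never dosed in the OLE | 169 | none | DB |
| Week 24 assessment two days before the OLE dose | 167 | 169 | DB |
| Deviation that began at Week 20 and is still ongoing | 141 | 169 | DB |

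Only the first case is misassigned, but it is the one the protocol's visit design produces for subjects who continue.

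**Step 3: the sections side by side.**

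- *SAP Table 1 against SAP 7.2.* A SALT I value obtained before the dose on Day 169 is DB data. A deviation in obtaining it, dated Day 169, is an OLE deviation.
- *SAP Table 2 against SAP 7.2.* The PPS definition removes any FAS subject with a major deviation that could affect the SALT I endpoints, in whichever period. It refers to SAP 7.2 for the working rule, and there exclusions come from the primary-lock review of DB deviations.
- *SAP 11.1 against SAP 7.2.* Adverse events have a pre-dose exception at Week 24; deviations have none.
- *SAP 7.2 and SAP Appendix 3.* The summary of deviations with possible SALT I impact is planned for the DB period only. The table of deviations that lead to PPS exclusion (14.1.3.2.1.2) is also DB only, with no OLE counterpart.

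**Step 4: which analyses use the PPS.** It is used in sensitivity analysis #3: observed-case MMRM for percent change and change in SALT I (SAP 10.1, 10.2), and the CMH test with non-responder imputation for the proportion endpoints (SAP 10.2). The primary analysis uses the FAS and does not depend on deviation labels.

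**The case against.** A reader might infer that a Week 24 deviation can never exclude a subject from the PPS. The documents do not go that far. The definition in SAP Table 2 is not limited to DB deviations, the list of excluding deviations in SAP 7.2 is open, and classification is referred to a deviation management plan that is not among these documents. By the primary lock, every subject has completed or left the DB period, so the deviation has already occurred and could be considered. The text is inconsistent; it is not an explicit bar. This stands.

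It can also be said that few deviations would matter. The four examples in SAP 7.2 (eligibility, wrong treatment, compliance below 80%, chronic prohibited medication) normally begin before Week 24. A missed SALT I puts no faulty Week 24 value into the observed-case model, although under non-responder imputation the subject counts as a non-responder. Protocol Table 9 speaks of missing more than a set number of visits, not one. An out-of-window visit is recorded as unscheduled and handled by the analysis windows. Nothing in the documents suggests that a scalp score would shift within a visit after one dose. This largely stands: a SALT I not done per procedure is the clearest case with real consequence.

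Finally, nothing is hidden. All deviations are listed, those with possible SALT I impact are flagged, and important and major deviations are also summarized overall on the Randomized Set. The study makes no formal type I error claim. This limits the severity. It does not explain why the label is wrong for DB data, or why adverse events have an exception that deviations lack.

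**Conclusion.** The point holds in a limited form. For subjects whose first OLE dose falls on the date of their Week 24 DB assessments, SAP 7.2 gives the wrong period to a deviation in those assessments. Read literally, it also leaves that deviation out of the blinded review that identifies PPS exclusions. This is at odds with SAP Table 1, SAP Table 2 and SAP 11.1.

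The effect reaches the PPS sensitivity analyses (#3) and the by-period deviation summaries, and nothing else. The primary FAS analysis is unaffected. Subjects never dosed in the OLE, subjects dosed on a later date, and deviations that began earlier are all labelled correctly.

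The number affected cannot be derived from the documents. A reader might take 78 × (1 − 0.15) ≈ 66 continuing subjects as the base for a percentage. That base is wrong: the PPS lies within the FAS, which requires baseline SALT I below 95, while Cohort 1 required only a score of at least 50. Not every completer need qualify for the OLE at Week 24 (Protocol 4.3), and the documents give no rate of Week 24 deviations.

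The conclusion rests on two assumptions: that such a deviation is dated to the visit day, and that the unseen deviation management plan does not already settle the matter.

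**What to change.** Add one sentence to SAP 7.2: a deviation dated on the day of the first OLE dose that concerns a double-blind (pre-dose) Week 24 assessment is a DB deviation and enters the blinded review before the primary lock. State in the same place that deviations in OLE eligibility, OLE dosing or post-dose procedures on that day remain OLE deviations. A rule covering everything at the Week 24 visit would wrongly pull those into the DB period.

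Check that the deviation management plan uses the same rule. The cost is that sentence and a flag in the deviation listing. It should be done before the primary lock, while PPS membership is still decided blind.

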8 PRIOR AND CONCOMITANT MEDICATIONS

Medications will be coded according to the World Health Organization Drug Dictionary (WHO-DD), September 2021 B3.

Prior medications are defined as any medication started and discontinued prior to the first study treatment dose. Concomitant medications are defined as any medication taken from the first study treatment dose throughout the end of the study including those who started prior to the first study treatment date and continued past that date. See Appendix 2 for handling of completely or partially missing dates for prior and concomitant medications. Concomitant medications taken on or after the first dose of study treatment during the DB Treatment Period and before the first dose of study treatment during the OLE Period, including those started before the first dose of study treatment during the DB Treatment Period and continued past that date, will be assigned to the DB Treatment Period. Concomitant medication taken on or after the first dose of study treatment during the OLE Period, including those started before the first dose of study treatment during the OLE Period and continued past that date, will be assigned to the OLE Period.

Incidence of prior medications will be tabulated by anatomical therapeutic chemical (ATC) level 3 and Preferred Drug Name based on the SAF. Subject with the same medication taken multiple times within the same Preferred Drug Name will be counted only once for that Preferred Drug Name. Similarly, if a subject has taken more than one medication within the same ATC level, then the subject will be counted only once for that ATC. Concomitant medications will be summarized similarly by study period.

A listing of all prior and concomitant medications will be provided.

9 STUDY TREATMENT EXPOSURE AND TREATMENT COMPLIANCE

Duration of exposure to study drug, in days, will be computed overall and for each study period as follows:

Overall duration of exposure = (Date of last dose of study drug, regardless of the study period –
Date of first dose of study drug during the DB Treatment Period)
+ 1

Duration of exposure for DB Treatment Period = (Date of last dose of study drug during the DB Treatment Period – Date of first dose of study drug during the DB Treatment Period) + 1

Duration of exposure for OLE Period = (Date of last dose of study drug during the OLE Period – Date of first dose of study drug during the OLE Period) + 1

Duration of exposure to etrasimod 2 mg and etrasimod 3 mg will also be computed overall and for the OLE Period as follows:

Overall duration of exposure to etrasimod 2 mg = (Date of last dose of etrasimod 2 mg, regardless of the study period – Date of first dose of etrasimod 2 mg, regardless of the study period) + 1

Overall duration of exposure to etrasimod 3mg = (Date of last dose of etrasimod 3 mg, regardless of the study period – Date of first dose of etrasimod 3mg, regardless of the study period) + 1

Duration of exposure to etrasimod 2 mg during the OLE Period = (Date of last dose of etrasimod 2 mg during the OLE Period – Date of first dose of etrasimod 2 mg during the OLE Period) + 1

Duration of exposure to etrasimod 3mg during the OLE Period = (Date of last dose of etrasimod 3 mg during the OLE Period – Date of first dose of etrasimod 3mg during the OLE Period) + 1

In addition, duration of dose interruptions (in days) will be calculated overall and by study period as follows:

Overall duration of dose interruptions =

$$\sum_{i=1}^n (\text{End date of dose interruption } i - \text{Start date of dose interruption } i) + 1$$

if subject has at least one dose interruption interval

0 if subject has no dose interruption intervals

where n = total number of dose interruption intervals during the whole study.

Duration of dose interruptions for the DB Treatment Period and OLE Period will be calculated similarly, but n will be the total number of dose interruptions during the DB Treatment Period and total number of dose interruptions during the OLE Period, respectively.

Compliance with study drug, in percentage, will be calculated overall and by study period as follows:

Compliance with study drug (%) for DB Treatment Period=

